### 3.5.5.2. Effect sizes and equivalence limits, where applicable

The effect size is discussed in detail under 'statistical design and analysis'.

### 3.5.5.3. Risks and anticipated adverse device effects that are to be assessed

Risks and anticipated adverse effects during the clinical trial are discussed in detail under 'Adverse events, adverse device effects and device deficiencies'. For a more detailed overview of all risks related to the investigational device we refer the reader to the IB.

## 3.5.6. Design of the clinical investigation

### 3.5.6.1. General

The main goal of this clinical study is to evaluate the efficacy of the ALICE app.

We will prove efficacy in two distinctive user groups:

- Experienced hearing aid/CI users (Dutch speakers: Research ARM 1, approved by EC on 25/08/2022 – ref. CIV-22-06-039801, French speakers: Research ARM 3)
- First-time hearing aid users (Dutch speakers: Research ARM 2, approved by EC on 20/02/2023 – ref. CIV-22-06-039801)

This clinical study is a multicenter study that takes place in different hearing aid centers and one university hospital. All investigational sites are geographically spread across Belgium.

The duration of the study is estimated between 12 and 26 months, between October 2022 and December 2024 (see procedures for the overview of the time lines).

### 3.5.6.2. Research ARM 1 (approved by EC on 25/08/2022 – ref. CIV-22-06-039801)

**Description of the design type of clinical investigation to be performed (e.g. comparative double-blind, parallel design, with or without a comparator group) with rationale for the choice**

The study design is a randomized controlled clinical trial (RCT) which is the golden standard for ascertaining the efficacy and safety of a new treatment or intervention. The goal of the current RCT is to demonstrate the superiority of the ALICE app, as a new intervention over the existing standard of care.

In this RCT two groups will be compared:

- (1) A group that receives the standard of care, which is defined as followed:
  - a. Persons with a moderate to profound HI who are provided with a hearing aid
  - b. Persons with a profound to severe HI who are provided with a cochlear implant and concomitant rehabilitation. Most persons with a cochlear implant receive intensive rehabilitation during the first 6 months after their implantation. Afterwards, they mainly return for mapping of the device but not for listening training therapy.
- (2) A group that receives the standard of care, supplemented with the ALICE app, to be used as a home-based monitoring, training and counselling tool.

Description of the measures to be taken to minimize or avoid bias, including randomization, concealment of allocation, blinding/masking, assessment of blinding plan and management of potential confounding factors

For each investigator site clients will be recruited by the local principal investigator (PI) of the study (HCPs working in the hearing centre or university hospital). Once the HCP has recruited the required number of clients, they will send the list of clients to the KU Leuven researcher who will divide the clients randomly across the two groups (standard of care/additional use of ALICE). Randomisations of these two groups will be stratified according to age and will be done automatically with an automatic seed generator.

We foresee a few possible confounding factors:

- Medical confounding factors
  - o Type and degree of HI
  - o Comorbidities such as high blood pressure, diabetes, stroke, visual acuity, cognitive abilities
- Methodological confounding factors
  - o For sentence understanding in noise, procedural effects are believed to be minimal. The LIST sentence materials will be offered twice, at first and final appointment. Lists of sentences are counterbalanced and never presented twice.
  - o Potential procedural effects for the questionnaires may occur and will be controlled for by administering the questionnaires twice prior to the participants starting the training and at the end of the 8 week training period.
- Other confounding factors such as lifestyle factors

#### Primary and secondary endpoints, with rationale for their selection and measurement

The outcome measures that will be used as an endpoint to determine the clinical benefit of the ALICE app are:

- Effectiveness of the app is ensured
  - o Enhanced speech understanding in difficult listening situations
  - o Enhanced communication strategies
  - o Reduced reported listening difficulties and reduced experienced listening effort
  - o Increased knowledge/acceptance of the non-auditory consequences of HI
  - o Increased satisfaction with hearing aid/cochlear implant

#### Methods and timing for assessing, recording, and analyzing variables

*Table 1. Overview of outcome measures of assessment during the study*

ALICE-Client			
	Outcome measure	Type of test	Name of test/questionnaire
Effectiveness	Speech understanding in difficult listening situations	Speech in noise test	LIST ([name] et al. 2008)
		Questionnaires	SSQ12 (Gatehouse and Noble, 2004) COSI (Dillon et al., 1997))
	Listening effort		EAS (Alhanbali et al., 2017)
	Emotional consequences /acceptance of HI		CAS (Öberg et al., 2021)
	Use of hearing aid		IOI-HA (Kramer et al., 2002)

#### *Overview of the tests and questionnaires used*

(all materials are added to the folder CIP materials)

The **LIST** (Leuven intelligibility sentences test) is a validated speech test, using sentences that can be used in quiet or in noise ([name] & Wouters, 2008). Each set consists of 10 sentences that are equally difficult. In the literature the initial test is sometimes performed at two different times to minimise the risk of procedural learning. This LIST is included in the investigation because it is commonly used in the standard clinical practice and is able to demonstrate off-task training effects for speech understanding in noise after using the ALICE app.

The **COSI** questionnaire (Client Oriented Scale of Improvement) is a validated clinical tool that can assist in measuring the impact of hearing aid fitting on a person's life and the benefit that is obtained after intervention (Dillon et al., 1997). Administering the COSI questionnaire is also part of the RIZIV application to receive a refund for hearing aids. The COSI questionnaire allows the audiologist to measure improvements in listening situations important for their client. Before fitting the hearing aids, together with their client, they list their client's needs/goals. After hearing aids have been fitted and the client has had time to experience the hearing aids, they evaluate the progression/satisfaction in these situations together with their client.

The **CAS** (Communication and Acceptance Scale) is a validated scale that consists of 18 items (Öberg et al., 2021). The CAS scale is a reliable instrument that can be used to measure the effect of a rehabilitation programme. Each question is scored on a 5-point Likert scale (completely agree to completely disagree). It was developed to detect clinical changes in "communication strategies and the emotional consequences, knowledge and acceptance of HI". This questionnaire has been translated from Swedish to Dutch (and back translated to ensure correct translation).

**EAS** (Effort Assessment Scale) is a validated scale to measure listening effort (Alhanbali et al., 2017). The EAS consists of 6 items that are scored by the client on a 10-point scale, no effort to lots of effort. The EAS questions were translated to Dutch for this study.

The **SSQ12** is a short version of the validated Speech, Spatial and Qualities of Hearing Scale. This short form was developed for use in clinical research and rehabilitation settings. (Noble et al., 2013). Participants score each questions on a ruler (visual analogue scale) from 0 to 10. Questions were translated to Dutch.

The **IOI-HA** (International Outcome Inventory for Hearing Aids) evaluates the daily use of the hearing aid, as well as the perceived benefit and satisfaction with the hearing aids or cochlear implants. The IOI-HA consists of 7 questions and has been validated in Dutch (Kramer et al., 2002).

**Equipment to be used for assessing the clinical investigation variables and arrangements for monitoring maintenance and calibration**

*Equipment used/needed to perform test protocol*

- Speech in noise testing: part of the standard of care
  - o Audiometer (calibrated): available at the investigational sites
- Questionnaires: online/tablet
  - o Clients will be able to fill out the questionnaires on a tablet (provided by the KU Leuven researchers to the investigational sites) or on their own computer through a website.
- The app will be used on the clients' personal smart device (device compatibility will be described in IB)
- Feedback: documented in word files

**Clinical investigation sites: number, location and if appropriate differences in clinical investigation site characteristics**

A list of participating clinical investigation sites and their locations will be provided at a later stage.

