#### ALICE-Pro

The ALICE-Pro dashboard is accessible from a website on a dashboard computer.

[figure not shown]
ALICE-Pro allows the HCP to gain insight in the listening and communication skills of their clients based on the data and results of the client app, i.e. results of monitoring tasks, listening training exercises (Pro Portal; Figure 2) and on daily life experiences of their clients (counselling module). The output of the counselling module includes information about the clients' well-being, their degree of self-management and difficulties they encounter in daily life.

This information provides the HCP with a systematic overview of the clients' results and needs that can be used as guidance during follow-up consultations.

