#### 3.5.3.2. Evaluation of clinical data relevant to the proposed clinical investigation

To date, no consensus exists on how effectiveness of AR should be assessed and a comparison across apps is impossible due to differences between languages. In the current study, a validated measure for speech understanding in noise is used as the main outcome, complemented with non-auditory outcomes to evaluate effectiveness in a broader context of functioning and participation.

Justification for the chosen materials:

- *A speech in noise test* (Dutch: LIST sentences or BLU words, French: Lafon's dissyllabic words) will evaluate the persons' ability to perceive speech in noise, in a clinically controlled condition.

Speech in noise understanding has been reported as the number one difficulty that persons with HI encounter in daily life.

We should keep in mind that sentence testing in noise only partly resembles real-life listening difficulties (well-articulated sentences in speech-weighted noise, whereas in real life, speech understanding is also influenced by high paced speech, interruptions by other talkers, and other acoustical factors such as background noise, reverberation, and cognitive factors). However, it is not possible to account for all real-life factors in a testing environment.

- Besides the clinically validated measures we will evaluate the daily life listening with *questionnaires* that tap into the listeners' daily life experience:
  - o We will evaluate perceived listening difficulties with the Speech Spatial and Quality of hearing questionnaire (SSQ12) which evaluates typical listening situations and is commonly used in clinical practice and the Client Oriented Scale of Improvement (COSI) which evaluates an individual's listening difficulties reported by the listener over time.

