#### Hypotheses on the clinical performance & effectiveness of the ALICE app

##### User-oriented outcomes for experienced HA/CI users

After 8 weeks of continued use of the ALICE-Client app persons with HI will:

- Indicate enhancement in their daily life listening and/or communication strategies (primary)
  - Enhanced speech understanding in difficult listening situations
  - Reduced listening effort
- Indicate to be more knowledgeable about their HI and recognize the emotional consequences of their HI (secondary)
- Indicate to be more satisfied with the delivered care and/or their hearing aid/cochlear implant in daily life (secondary).

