## Monitoring plan

*General outline of the monitoring plan to be followed, including access to source data and the extent of source data verification planned*

In accordance with ICH-GCP E6(R2) the Sponsor is responsible for monitoring the Trial to ensure compliance with GCP and current legislation, and to verify, among other requirements, that proper written informed consent has been obtained and documented, that the Trial procedures have been followed as shown in the approved protocol, and that relevant Trial data have been collected and reported in a manner that assures data integrity. To this end Source Data will be compared with the data recorded in the (e)CRF. A risk-based approach will be applied to determine the extent of monitoring activities and monitoring of the Trial will be performed by qualified individuals (independent from the site Trial staff), as applicable.

- **Coordination & monitoring plan**

- o Project management and on-site monitoring visits

The Coordinating Investigator ([name], KUL) will supervise: the recruitment and the enrolment of the study participants (including the verification of the ICF procedure), the implementation of the study protocol at the investigational sites, the quality of the data collection, the achievement of the study goals, and the use of the ALICE app according to the CIP.

The test protocol will be performed by the local PI. The local PI can rely on support and assistance of the Coordinating Investigator at any given time. The Research Manager will schedule regular monitoring visits with the local PI. All monitoring activities will be documented in a written report according to ISO14155.

- o Project support

When clients need additional support their first contact point will be their local PI. When the support needed is related to their hearing or hearing aids, the local PI will help them out through their standard of practice (standard care path).

When the support needed is related to the use of the app, the local PI will contact the Coordinating Investigator. The Coordinating Investigator will provide the local PI with additional support, if needed technical support will be provided by our in-house developers.

- o Safety evaluation & reporting

- Adverse events, device deficiencies, and withdrawals will be reported and documented (see section 'Subjects' + withdrawal procedure section 3.5.6.2).
- Data collection

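### The plan does not settle who rates the final COSI; if rated jointly, as its description says, the rating is open to detection bias towards the app

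*Combined protocol and SAP*

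**What the plan says.** **How the COSI is rated.** The overviews of tests and questionnaires in sections 3.5.6.2 (Arm 1) and 3.5.6.3 (Arm 2) use the same text: "The COSI questionnaire allows the audiologist to measure improvements in listening situations important for their client". Once the client has had time with the hearing aids, "they evaluate the progression/satisfaction in these situations together with their client". Section 3.5.6.4 (Arm 3) refers back to this account.

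**What points to client report.** Section 3.5.3.2, which justifies the chosen measures, describes the COSI as tracking difficulties that the listener reports. The equipment list in each arm says: "Clients will be able to fill out the questionnaires on a tablet", or on the client's own computer through a website. These lists neither name nor exempt the COSI.

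**Where the COSI sits among the outcomes.** Table 1 (Arm 1) lists it beside the SSQ12 as a questionnaire for speech understanding in difficult situations. Section 3.5.5.1 makes that a sub-item of "Indicate enhancement in their daily life listening and/or communication strategies (primary"). Section 3.5.3.2, however, says that "a validated measure for speech understanding in noise is used as the main outcome, complemented with non-auditory outcomes".

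**Who is involved.** Under the monitoring plan, "The test protocol will be performed by the local PI". The local PI also leads onboarding, and app installation is listed in the same study programme. The ALICE-Pro section says that the dashboard gives the professional an overview of results and needs "that can be used as guidance during follow-up consultations". Section 3.5.2.3 confirms that professionals follow clients on this dashboard during the study.

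**The concern.** A questionnaire scored jointly with a professional is partly that professional's judgement. Here the professional would know the allocation and, for one group only, would have seen a record of training results, listening tests and daily-life answers before or during the final conversation. A control client brings no such record. Encouraging dashboard results could therefore lift the final COSI in the ALICE group without any change in the client's own experience. That is detection bias, and it would favour the app.

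Leaving the mode open has a second cost. Sites could reasonably follow either description, so the mode could differ between sites, or between groups within a site, without any protocol deviation.

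**Working it through.** The plan states no figure on this point, so the main check is a comparison of texts.

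1. **Is the COSI described differently from the other questionnaires?** Yes. The EAS and SSQ12 are described as scored by the client or participant. The COSI is described as evaluated by audiologist and client together.
2. **Is that description a trial procedure?** Not clearly. It follows the usual sequence of goals before fitting and review afterwards. That suits Arm 2. Hearing aid users in Arms 1 and 3 have already finished their trial period and decided to buy, so for them it cannot literally describe the visits at 0 and 8 weeks.
3. **Does other text settle the mode?** No. Section 3.5.3.2 and the equipment lists lean towards client report, but the equipment wording only says that clients can use the tablet or website. It does not say that the COSI must be completed alone.
4. **Would a joint rater know the group?** Almost certainly. The local PI performs the tests and leads onboarding. The bias subsections of all three arms name blinding in their headings but describe no masking underneath.
5. **Is the rater's information unequal between groups?** Yes, by inference. Dashboard content comes from the client app, which only the ALICE group receives.

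**Illustration of size.** The documents give no value for such bias, so the shift is assumed. Suppose no true effect and a shift of b SD in the ALICE group, tested with a two-sample t-test at two-sided α = 0.05:

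- noncentrality = b × √(n/2), with 2n − 2 degrees of freedom
- false-positive rate = P(|T| > critical value), T following the noncentral t distribution

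Group sizes are those for hearing aid users in section 3.5.7.1.

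| n per group | Critical t | b | Noncentrality | False-positive rate |
|---|---|---|---|---|
| 60 (Arms 2, 3) | 1.980 | 0.1 | 0.548 | 8% |
| 60 | 1.980 | 0.2 | 1.095 | 19% |
| 60 | 1.980 | 0.3 | 1.643 | 37% |
| 75 (Arm 1) | 1.976 | 0.1 | 0.612 | 9% |
| 75 | 1.976 | 0.2 | 1.225 | 23% |
| 75 | 1.976 | 0.3 | 1.837 | 45% |

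The test is a simplification: section 3.5.7.2 plans a repeated measures ANOVA with Holm-corrected post-hoc tests.

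**The case against.** The strongest reply is that the joint-rating sentence is background on how the COSI is normally used, while the trial-specific text points to self-completion. Table 1 classes the COSI as a questionnaire, questionnaires are listed as online or tablet, and section 3.5.3.2 calls it listener-reported. The equipment wording can be read as a choice between two devices rather than as optional self-completion. The form itself is in the study materials folder, which was not available here. This stands to the extent that a reader should not infer that the trial does rate the COSI jointly. It does not close the gap, because the plan's only detailed account of COSI scoring is the joint one.

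A reader might also infer that the trial's primary result is at risk. The documents do not support that. The COSI's primary status comes only from reading section 3.5.5.1 together with Table 1. The Arm 1 endpoint list labels nothing primary, section 3.5.3.2 names speech in noise as the main outcome, and the power analysis is for speech in noise.

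Nor should an assumed shift be set against the 0.25 in section 3.5.7.1. That effect size concerns a different outcome, and its scale is unclear: the total of 76 can be reproduced if 0.25 is read as Cohen's f (two groups, two times, assumed correlation 0.3), whereas a plain two-group d of 0.25 would need 832.

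Finally, clients know their group, so self-completion leaves their own expectations in the rating. That is true, but the professional's influence is a separate source and can be removed.

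**Conclusion.** The point holds as a conditional one. The plan describes the COSI as jointly evaluated in one place and as client-reported or client-completed in others, so the mode is not settled. If it is joint, the rater's knowledge of allocation and one-sided access to ALICE-Pro open the rating to detection bias towards the app.

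The size is unknown. The rates of 8% to 45% follow mechanically from assumed shifts of 0.1 to 0.3 SD and are illustrative only; they are not estimates for this trial. The conclusion rests on two inferences: that the rater is unmasked, since no masking is described and the local PI leads onboarding, and that controls have no dashboard data, since they have no app. It is a low-cost improvement worth making. It does not show that the trial's results would be invalid.

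**What to change.** Reconcile the passages. In the COSI descriptions for Arms 1, 2 and 3, state that the client alone enters the final study ratings on the tablet or website already provided, before the consultation and before any ALICE-Pro results are discussed. The situations to be rated may still be chosen together at the first visit. Where a jointly rated COSI is needed for the reimbursement application, keep it separate and do not analyse it. Repeat the rule in site training.

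This takes a short statement per arm and no extra staff or equipment. The downsides are a small departure from the usual joint mode of the COSI and possibly a second COSI form for Arm 2 clients. It does not mask the client. Nor does it mask the joint choice of situations, because the first assessment comes after allocation.

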## Subjects

Subjects will be recruited by their HCP (see recruitment procedure) in accordance with the following criteria:

### *Inclusion criteria*

- Clients who are using a hearing aid (N = 150) or cochlear implant (N = 30). Which is more than necessary according to the power analysis (3.5.7).
  - o Clients with a hearing aid must have completed the hearing aid trial period and must have decided to purchase the hearing aid.
  - o Clients with a cochlear implant must have at least 6 months of experience with the cochlear implant.
- Clients who experience listening and communication difficulties
- Clients with a hearing aid may not have any experience with auditory training yet.
- Able to operate the training programme as an app on a mobile device/tablet (e.g. clients have a mobile device or table; clients have sufficient eyesight to see the exercises; clients must be able to operate the programme).
- At least 18 years old.
- Dutch-speaking as all training material and counselling questions will be presented in Dutch.
- Clients need to have an Android or iPhone smartphone and connection to internet

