### *Whether and how subjects are to be replaced.*

In case of withdrawal or loss to follow up, we will report this but the client will not be replaced since we have sufficient participants for the study.

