#### *Recruitment of clients*

- Local PIs will be responsible for the recruitment of patients. Before they start with recruiting they will be instructed with clear inclusion and exclusion criteria (see 3.5.6.2 Subjects)
- The number of clients that should be enrolled will be in the range of 20-30 for every investigator site
- The recruitment period is a fixed period over a time span of 12 weeks or when 20 to 30 clients are recruited (start of the study + 12W), after that period no clients can enter the study.

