### 3.5.7. Statistical design and analysis

#### 3.5.7.1. Sample size

HCPs from the hearing centres participating in the first, second and third arm of the study will include a total of 390 hearing aid users (150 in the first arm, 120 in the second arm and 120 in the third arm). HCPs from UZ Leuven will include 30 CI users for the first arm only. Clients will be equally divided among participating investigation sites. After being stratified by age, they will be randomly assigned to two groups of approximately 195 hearing aid users (75 in the first arm, 60 in the second arm and 60 in the third arm), and two groups of 15 CI users (first arm only). One group will receive the standard of care, the other group will receive the standard of care supplemented with the ALICE app (The Dutch version in both the first and second arm the French version in the third arm).

Scientific literature was consulted to estimate the group size needed for our RCT and a power analysis was conducted to confirm the effect size for this sample.

Power analysis conducted with the G\*Power software (Erdfelder et al., 2009) indicated that a total sample of at least 76 persons is needed to detect differences in speech understanding in noise outcomes between the two treatment groups with a low to medium effect size ( $d = 0.25$ ) to have statistical power of 95% using a repeated measures ANOVA ( $\alpha = 0.05$ ). We will be able to recruit more clients via the hearing centers (between 15 and 30 persons per hearing center). We estimate that, for all three arms of the study, 390 persons with a HA will take part in the trial and, for the first arm of the study only, about 30 persons with a CI. This larger number accounts for clients being lost to follow-up during the study.

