#### 3.5.7.2. Statistical analysis

Statistical analyses will be performed using either the R programming language and statistical environment (R Core Team, 2017) or IBM SPSS 27. Potential missing data will be replaced using multiple imputation (in SPSS).

Data for hearing aid users and cochlear implant users will be analysed separately. Potential relations between outcomes will be determined in a within-subject design, i.e., baseline session outcomes will be compared to the final session outcomes, with a repeated measures ANOVA ( $\alpha = 0.05$ ). We will correct for multiple comparisons using Dunn post-hoc tests with Holm correction (Dunn, 1961).

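### Arm 1 recruitment is called more than the power analysis requires, yet the separate cochlear implant analysis has 30 people against a stated minimum of 76, with no justification or exploratory label

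*Combined protocol and SAP*

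**What the plan says.** The Arm 1 inclusion criteria (section 3.5.6.2) put both device groups into one adequacy statement. Clients are those "using a hearing aid (N = 150) or cochlear implant (N = 30). Which is more than necessary according to the power analysis". The replacement rule in the same section draws on it: on withdrawal, "the client will not be replaced since we have sufficient participants for the study".

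The plan has one power analysis, in section 3.5.7.1. It concludes that "a total sample of at least 76 persons is needed" to detect a difference in speech understanding in noise between the two treatment groups. The inputs are an effect size of 0.25 (labelled d), 95% power, a repeated measures ANOVA and alpha 0.05. The same section splits the 30 implant users into two groups of 15. Of the planned recruitment it says: "This larger number accounts for clients being lost to follow-up during the study".

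Section 3.5.7.2 then states: "Data for hearing aid users and cochlear implant users will be analysed separately". The Arm 1 design paragraph sets the aim: "The goal of the current RCT is to demonstrate the superiority of the ALICE app". Its definition of standard of care covers both hearing aid and implant users.

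**The concern.** A sample size is adequate or not for a particular comparison. Because the device groups are analysed apart, no planned Arm 1 test uses all 180 people. The implant test uses 30, and the only minimum on offer is 76. The two supporting reasons fail for this group as well: there is no surplus to absorb losses, and the participants are not sufficient by the plan's own standard.

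What is at stake is how the implant result will be read. The plan writes no separate implant claim, but it will test that group on its own. A reader told that recruitment exceeds the requirement could take a non-significant implant result as evidence that the app does not help implant users.

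**Working it through.** **Direct comparison, with no assumptions.** Inputs: 150, 30 and 15 per group (Arm 1 inclusion criteria and section 3.5.7.1), minimum 76 (section 3.5.7.1), separate analysis (section 3.5.7.2).

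- Arm 1 total: 180/76 = 2.37.
- Hearing aid users: 150/76 = 1.97.
- Implant users: 30/76 = 0.39, a shortfall of 76 − 30 = 46.

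**Reproducing 76.** The plan does not state the correlation r between the two visits or the G\*Power settings. I used the noncentral F for the group-by-time interaction with k groups and m = 2 visits: lambda = f² × N × m/(1 − r), df = (k − 1) and (N − k), alpha 0.05. I read 0.25 as Cohen's f, which is an assumption because the plan writes d.

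- k = 2, r = 0.3, N = 76: lambda = 0.0625 × 76 × 2/0.7 = 13.57; power 0.953. With two groups, 76 is the minimum even N only for r of about 0.29 to 0.31.
- k = 2, r = 0.5: the minimum is 54, not 76.
- k = 4, r = 0.5: N = 76 gives lambda = 19.0 and power 0.959; N = 72 gives 0.948. This setting also returns 76.

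**Power of the implant comparison (k = 2, f = 0.25).** The 24-completer column is illustrative (20% loss), since the plan states no loss rate.

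| r | lambda at N = 30 | Power, N = 30 | Power, 24 completers |
|---|---|---|---|
| 0.3 | 0.0625 × 60/0.7 = 5.36 | 0.61 | 0.51 |
| 0.5 | 0.0625 × 60/0.5 = 7.50 | 0.75 | 0.65 |

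**Could a higher correlation make 30 enough?** Power at N = 30 reaches 0.95 at r of about 0.73. The minimum would then be about 30 to 32, not 76, so no single r supports both numbers.

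**Precision.** In a 2 × 2 interaction, f = 0.25 means cell effects of ±0.25 SD, so the difference in change is 4 × 0.25 = 1.0 SD. The change score has SD √(2(1 − r)), and its two-group test is equivalent to the planned interaction test. With 28 df (t = 2.048), the 95% confidence interval half-widths are:

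- r = 0.3: 2.048 × 1.183 × √(2/15) = 0.89 SD.
- r = 0.5: 2.048 × 1.000 × √(2/15) = 0.75 SD.

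At r = 0.3, 30 people detect a difference in change of 1.25 SD with 80% power and 1.61 SD with 95%.

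**If 0.25 is literally d.** Taking it as 0.25 SD on the change scale, with r from 0.3 to 0.8, power is 9% to 18% at N = 30 and 25% to 67% at N = 150.

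**The case against.** The strongest reply is that the statement describes Arm 1 as a whole. The 150 and the 30 stand in one bullet, the minimum is a total, and 180 exceeds 76. A four-group entry in G\*Power would fit that reading, since Arm 1 has two hearing aid and two implant groups. The hypotheses in sections 3.5.4.1 and 3.5.5.1 also treat experienced hearing aid and implant users together, so no implant-specific claim depends on these 30 people. On this view the sums are right and only the scope is unclear.

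Part of this stands. The wording is true of the total, and the fault lies in the fit between sections rather than in a miscalculation. But section 3.5.7.2 plans no pooled analysis to which a total of 180 could apply, and the bullet names the 30.

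A second reply is that 76 is itself undocumented, so measuring against it proves little, and a literal d of 0.25 would leave the hearing aid group short too. That is fair as to the size of the power deficit, which can only be given as a range. It does not rescue the statement, because 76 is the standard the plan invokes. A third reply is that literature was consulted (section 3.5.7.1) and that an earlier 40-person implant trial is described (section 3.5.3.1). Neither is offered as a reason for 30.

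**Conclusion.** The concern holds. Measured against the plan's own minimum, the separately analysed implant comparison has 30 of 76 (39%), 46 short before losses. It has no sample-size reason of its own and no exploratory label. That conclusion rests on the documents alone.

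The power figures are conditional. With 0.25 read as f and the correlations at which 76 can be obtained, two-group implant power is about 61% (r = 0.3) to 75% (r = 0.5, where 76 requires four groups to be entered). The corresponding 95% confidence interval is about ±0.89 to ±0.75 SD on the difference in change. A non-significant implant result would be compatible with a worthwhile benefit. Nothing here confirms 76 or affirms that 150 hearing aid users are enough.

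**What to change.** - In the Arm 1 inclusion criteria and replacement rule, stop applying the adequacy statements to the implant analysis. Keep them for hearing aid users only if 76 is substantiated by stating the effect metric, r and the G\*Power settings.
- If implant withdrawals are not replaced because the entry window closes (under recruitment of clients, "after that period no clients can enter the study"), give that as the reason.
- In section 3.5.7, state that the implant analysis at N = 30 does not meet the minimum of 76. Give its power or detectable difference under the planned repeated measures ANOVA and the same assumptions that produce 76.
- Report the implant treatment difference with its 95% confidence interval as exploratory, with no separate superiority claim, and do not interpret a null result as no benefit.

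This costs wording in three places, with no extra participants and no change of analysis method. The implant conclusion becomes softer. If Arm 1 data already exist, date the change so that the exploratory label is not taken as a response to the results.
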